1.1.1.2 Secondary objective

- To analyze the short term (1 year) safety of the MHP compared to the Stanmore hip replacement.
- To analyze the short term (1 year) efficacy of the MHP compared to the Stanmore hip replacement.
- To analyze the long term (10 years) safety of the MHP compared to the Stanmore hip replacement.
- To analyze the long term (10 years) efficacy of the MHP compared to the Stanmore hip replacement using patient based questionnaires.

Study design: Single-centre prospective study with 25 patients in the study and 25 in the control group. Open, RCT (Randomized Controlled Trial) in which the MHP is compared with the standard Stanmore hip prosthesis.

Study population: Patients with osteoarthritis of the hip with no severe co morbidities.

Main study parameters/endpoints:

- Stability measured with RSA at discharge, 3, 6, 12 and 24 months postoperative.
- Safety defined as absence of serious device related complications.
- Efficacy defined as functional outcome measured with HHS and the HOOS preoperatively, 6 weeks, 3, 6 and 12 months and subsequently annually at 2-7 years and at 10 years postoperatively.
- Bone density measured using DEXA preoperative and 6 weeks, 1, 2 years postoperative.
- Quality of life measured with the SF12 preoperatively, 6 weeks, 3, 6 and 12 months and subsequently annually at 2-7 years and at 10 years postoperatively.

Nature and extent of the burden and risks associated with participation, group relatedness:

The MHP has not been implanted in human before. Therefore risks of the MHP in vivo are unknown. Nevertheless, preclinical tests of the MHP showed promising results.

All potential risks for a hip prosthesis are reported in section A4.4.

For the study additional traditional and RSA X-rays need to be made, as well as additional DEXA scans. Therefore the radiology exposure will increase with 6 mSv for the total study (10 years). The average annual natural dose is 2 mSv.

The questionnaires will take approximately 10 minutes at each control visit. The RSA and DEXA scans will take approximately 15 minutes each.

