2 STATISTICAL ANALYSIS PLAN

Statistical design, method and the analytical procedures

The patient characteristics of both groups will be compared using the chi square test for categorical data, the t-test for normal divided continuous data and non parametric test for not normally divided continuous data.

If the patient characteristics are not significantly different, no correction will be made, otherwise the data will be corrected using multiple variation analysis.

Continuous outcome variables will be analyzed with general linear modelling which a Bonferoni post hoc test and the data will be compared to the preoperative data.

Clinical data (HHS, HOOS and SF-12) will be presented using 95% confidence intervals while comparing the results between the MHP and Stanmore prostheses.

Differences in the various clinical and laboratory outcomes between treatment groups will be presented with their 95% confidence intervals.

b) Sample size

50 patients. 25 in each group.

This item is described in session A.5.2

c) Level of significance and the power of the clinical investigation

Not relevant, since the power is based on literature (session A 5.2).

d) Expected drop-out rates

Not relevant, since the power is based on literature (session A 5.2).

e) Pass/fail criteria to be applied to the results of the clinical investigation

Table 2: Criteria for decision to continue the study.

	Pass
Safety:	Less than 10% device related complications.
Efficacy	Functional improvement and pain reduction measured with the Harris Hip Score and HOOS compared to preoperative score within the same range as the improvements for the Stanmore hip.
Correctly implanted	Based on standard radiographs 
- A leg length increase between -10 and 5 mm.- Laterization of the head between + 5 and -10 mm.- Circumferential cement mantle.- The bone plug is placed 1 to 3 cm below the prosthesis.

	
- Absence of cement leakage below plug.- Absence of radiolucency between prosthesis and cement in all Gruen zones.
--	---

f) Provision for an interim analysis, where applicable

After 20 patients are included (10 MHP and 10 Stanmore), a 6 weeks waiting period will be used after which the surgeon will decide if the prosthesis is safe according to criteria defined above. An independent orthopaedic surgeon will evaluate the X rays of the first 10 patients with the MHP prosthesis.

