g) Criteria for the termination of the clinical investigation on statistical grounds

- A significant decrease in functional improvement in the MHP group compared to the Stanmore group.
- A significant increase in complications and adverse events in the MHP group compared to the Stanmore group.

h) Procedures for reporting any deviation(s) from the original statistical plan

The used statistical technique depends on the deviation of the variables. Therefore, the exact statistical technique will be determined during the evaluation and will be described in the report.

i) Specification of subgroups for analysis

The first 20 patients will be analyzed for adverse events and function to decide whether the study will continue.

j) Procedures for accounting for all data

The data will be monitored for completeness. If data is complete the file will be closed. If corrections to data are made after closure, the reason for change will be noted. If data is missing the cause will be noted on a specific document. After analysis the number of patients in each subgroup at each time interval will be noted in the tables.

k) Treatment of missing, unused or spurious data, including drop-outs and withdrawals

The study will be performed according to the intention to treat principle. If the patient is revised the last measured data will be carried forward. The data will be analyzed using general linear modelling which can account for some missing data.

l) A justification for excluding particular information from the testing of the hypothesis

Not relevant.

m) In case of multi-centre clinical investigations, the minimum and maximum number of subjects to be included for each centre

Not relevant.

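### SAP items (a) and (k) leave missing data to an unspecified general linear model that, in its usual forms, does not do what (k) claims; name a linear mixed model and fix it in (h)

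*Combined protocol and SAP*

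**What the plan says.** The opening section of the SAP (Statistical design, method and the analytical procedures, item (a) by position) analyses continuous outcomes with "general linear modelling which a Bonferoni post hoc test and the data will be compared to the preoperative data". It names no visits, covariance structure, estimation method or missingness assumption.

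Item (k) makes three statements: "The study will be performed according to the intention to treat principle"; "If the patient is revised the last measured data will be carried forward"; and "The data will be analyzed using general linear modelling which can account for some missing data". Only revision has its own rule.

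Item (j) requires the cause of missing data to be recorded and adds: "After analysis the number of patients in each subgroup at each time interval will be noted in the tables". That is a reporting rule and does not say how the data are analysed. Item (h) leaves the choice of technique until the evaluation, to be described in the report. Item (d) gives no drop-out rate and points to section A 5.2, which is not in the supplied text.

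The synopsis (Main study parameters/endpoints) sets long schedules. RSA has five examinations, from discharge to 24 months. For DEXA: "Bone density measured using DEXA preoperative and 6 weeks, 1, 2 years postoperative". HHS, HOOS and SF-12 are taken preoperatively, at 6 weeks and at 3, 6 and 12 months, then "subsequently annually at 2-7 years and at 10 years postoperatively".

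**The concern.** Item (k) depends on a property of the model, namely that it copes with incomplete patients. Whether it does depends on the form chosen.

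- Classical repeated-measures GLM needs every visit in the model and deletes any patient who lacks one. That runs against intention to treat.
- A separate linear model per visit keeps everyone seen at that visit but makes no use of the patient's other postoperative visits. It is valid only if missingness depends on nothing beyond what that model adjusts for.
- A model on all observed visits would serve the purpose of (k), but the plan does not name one.

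The choice decides which patients and visits enter the MHP minus Stanmore contrast. Because (h) postpones it, it can be made with the data in view, in an open trial of 25 patients per arm.

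**Working it through.** **Inputs from the documents.** 25 patients per arm. RSA: 5 examinations. DEXA: preoperative plus 3. HHS, HOOS and SF-12: preoperative, then 4 visits to 1 year, 6 at years 2 to 7, and 1 at year 10, so 4 + 6 + 1 = 11 postoperative visits. The plan states no figure on this point to reproduce.

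**Assumed, because the documents give no rate.** Misses of 2% to 5% per visit; preoperative visit complete unless stated.

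**Step 1: repeated-measures GLM with listwise deletion.** With independent misses at rate p over V visits, the share kept is (1 − p)^V.

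| Model | V | p = 2% | p = 5% |
|---|---|---|---|
| RSA to 24 months | 5 | 0.98^5 = 90% | 0.95^5 = 77% |
| DEXA, postoperative scans | 3 | 0.98^3 = 94% | 0.95^3 = 86% |
| Clinical data to 1 year | 4 | 0.98^4 = 92% | 0.95^4 = 81% |
| Clinical data, one 10-year model | 11 | 0.98^11 = 80% (40 of 50) | 0.95^11 = 57% (28 of 50) |

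If the preoperative visit is missed at the same rate (V = 12), the last row becomes 78% and 54%. If misses cluster within patients (beta-binomial, a + b = 1/ρ − 1, p = 5%, V = 11), the share kept is 68%, 75% and 80% at ρ = 0.1, 0.2 and 0.3.

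**Step 2: precision.** The half-width of the 95% interval in SD units is t(0.975, 2n − 2) × √(2/n), with n per arm. At p = 5%:

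- all patients seen at a visit, n = 25 × 0.95 = 23.75: 0.58 SD
- after 4-visit deletion, n = 25 × 0.95^4 = 20.36: 0.63 SD
- after 11-visit deletion, n = 25 × 0.95^11 = 14.22: 0.77 SD

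**Step 3: per-visit model, random misses.** No patient seen at the visit is lost. By simulation at 25 per arm, with 5% random misses, the standard error of the 10-year contrast is 0.281 SD for a per-visit model adjusted for the preoperative score and 0.274 SD for a mixed model with the true covariance. The difference is 0.007/0.281, between 2% and 3%. With 5% monotone drop-out per visit the figures are 0.359 and 0.328 SD.

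**Step 4: per-visit model, drop-out that depends on scores.** Simulation with 200,000 per arm, true difference 0, SD 1, preoperative-postoperative correlation 0.3, and three sets of postoperative correlations (0.30–0.63, 0.50–0.73 and 0.63–0.83). Drop-out is monotone from the second postoperative visit, and its odds double per SD of worse last score in one arm only. Ranges cover unadjusted, change-score and preoperative-adjusted models.

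| Drop-out per visit | Still seen at 1 year | Bias at 1 year | Still seen at 10 years | Bias at 10 years |
|---|---|---|---|---|
| 2% | 0.98^3 = 94% | 0.01 to 0.04 SD | 0.98^10 = 82% | 0.00 to 0.09 SD |
| 5% | 0.95^3 = 86% | 0.03 to 0.08 SD | 0.95^10 = 60% | 0.00 to 0.21 SD |

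At 5% drop-out the 10-year half-width is 0.75 SD (n = 25 × 0.60 = 15), so the largest bias is 0.21/0.75 = 28% of it. If the dependence is the same in both arms, the bias is at most 0.007 SD. A mixed model with unstructured covariance gave at most 0.004 SD in the one-arm scenario. Over 12 visits that structure needs 12 × 13/2 = 78 covariance parameters, too many to plan on with 50 patients.

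**The case against.** **The worst listwise figure belongs to an analysis the plan does not describe.** This stands. A reader might infer that the trial will shrink to 28 of 50 patients. The synopsis separates the 1-year and 10-year objectives, (j) promises counts at each interval, and (k) says the model tolerates some missing data. A single 10-year listwise model fits poorly with all three. The text does not exclude listwise deletion, but for RSA, DEXA and the 1-year data the loss is modest.

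**The per-visit reading suits the text better and does little harm.** This largely stands. With random misses the mixed model gains about 3%. A reader might infer that the contrast will be biased by 0.2 SD. That needs drop-out driven by earlier scores in one arm only, and about 40% drop-out by 10 years. The documents show neither, nor a direction.

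**The authors may have meant a mixed model.** Possibly, but (a) and (k) do not say so and (h) reserves the choice.

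**Item (d) leaves drop-out out.** A reader might infer that no allowance was made. Section A 5.2 is not supplied, so that cannot be concluded.

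**Carry-forward scope and deaths.** A reader might see these as further errors. The unrestricted wording of (k) most plainly covers all outcomes, and deaths can fall under its general provision. More detail would help, but the point does not rest on it.

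**Conclusion.** The point holds as a recommended change. The missing-data provision in (k) rests on a property that a general linear model lacks in its two usual forms, and (h) leaves the form open until the evaluation.

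The size depends on assumed rates. The clearest consequences are the loss of 10% to 23% of patients for RSA and 8% to 19% for the 1-year clinical data if the listwise form is used at 2% to 5% misses per visit. For the per-visit form the consequence is a possible bias, within sampling error even in the worst case examined and about 0 if drop-out behaves alike in both arms.

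A reader might also infer that a mixed model would keep the 10-year bias within 0.01 SD. That is not shown: the near-zero result came from an unstructured covariance, which is not realistic for the 12-visit series. The case for the mixed model is that it uses all observed visits under a stated missing-at-random assumption.

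**What to change.** - **Items (a) and (k).** Replace general linear modelling with a linear mixed model for repeated measures: REML, treatment by visit, all observed visits of all randomised patients, the preoperative value included where collected (HHS, HOOS, SF-12, DEXA), and a small-sample degrees-of-freedom method. State that the analysis is valid if data are missing at random. Name the covariance structure and a fallback in advance.
- **Item (h).** Fix this model before the data are seen and require any departure to be reported as a deviation. Without this, a model named in (a) and (k) could still be replaced at evaluation.
- **Item (k).** Add one sensitivity analysis with post-revision values set to missing instead of carried forward.

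The cost is SAP wording and standard software, with no extra data or patient burden. The downside is that a covariance structure must be chosen with 25 patients per arm. In simulation with correlation decaying over time, a compound-symmetry fallback shifted the 10-year contrast by about 0.03 SD relative to a random intercept with spatial-power correlation. If misses are random, the gain over per-visit models is small.
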